2.3 Rationale for dose and regimen selection

[figure not shown]
The LEE011 dose will be 600 mg QD for 21 days followed by a one week break as established in the [[CLEE011X2101](#)] study (28 day cycle). The MTD of LEE011 administered as single agent is 900 mg QD for 21 days followed by a one week break; however, the recommended dose for future development is 600 mg QD (3 weeks on/1 week off schedule) due to lower risk for QTcF prolongation, acceptable safety profile, adequate exposures, and preliminary evidence of clinical activity.

2.4 Rationale for choice of combination drugs

Not applicable

2.5 Rationale for choice of comparators drugs

Not applicable

[figure not shown]

3 Objectives and endpoints

[figure not shown]
Objectives and related endpoints are described in Table 3-1 below.

Table 3-1 Objectives and related endpoints

[figure not shown]
Objective	Endpoint	Analysis
Primary		Refer to Section 10.4
To assess the efficacy of LEE011 compared to placebo in patients with relapsed/refractory teratoma with recent progression	PFS as per RECIST v1.1 (by local investigator assessment).	
Secondary		Refer to Section 10.5.2 and Section 10.5.3
To assess other measures of efficacy of LEE011 compared with placebo	BOR, ORR, DOR, DCR at 4 months as per RECIST v1.1 and OS, OS Rate at 12 months.	
To assess safety and tolerability of LEE011 compared with placebo	Incidence and severity of adverse events and serious adverse events, changes in laboratory values, electrocardiograms, and vital signs will be used to assess the safety as per CTCAE v.4.03. Dose interruptions and changes will be used to assess the tolerability.	

[figure not shown]
[figure not shown]

4 Study design

[Redacted text]

4.2 Timing of interim analyses and design adaptations

No formal interim analysis will be conducted for this study.

4.3 Definition of end of the study

The study data will be analyzed and a primary clinical study report (CSR) will be written based on all patients' data at the time when there are approximately 23 PFS events for the primary efficacy analysis and all patients have been followed for PFS for at least 6 months or have discontinued prior to this time for disease progression or death, or have withdrawn consent to follow-up, or have been lost to follow-up (see [Section 10.4.2](#)), or enrollment in the LEE011 rollover clinical trial (CLEE011X2X01B), or early study termination, whichever occurs first. Additional data for patients continuing on study or in any survival follow-up period past the data cutoff date for the primary CSR will be reported in a final CSR once the treatment period, safety follow-up, disease progression follow-up and survival follow-up periods have ended for all patients as described in [Section 7.1.4](#). In the case when the study is terminated early (Section 4.4) and no CSR has been already reported, all data prior to the study termination will be reported in a final CSR (see [Section 4.4](#)).

4.4 Early study termination

The study can be terminated at any time for any reason by Novartis. Should this be necessary, patients should be seen as soon as possible and the same assessments should be performed as described in [Section 7.1.3](#) for an EOT/premature withdrawal patient. The investigator may be informed of additional procedures to be followed in order to ensure that adequate consideration is given to the protection of the patient's interests. The investigator will be responsible for informing IRBs and/or ECs of the early termination of the study.

5 Population

5.1 Patient population

The study will be conducted in patients, 15 years old or older, with a diagnosis of teratoma that have radiographic progression within 12 weeks of enrollment.

Patients who do not meet all the inclusion or exclusion criteria can be re-screened once for consideration in the trial. If a patient is re-screened, the same patient ID number should be used.

Patients enrolled in this study are not permitted to participate in additional parallel investigational drug or device studies.

The investigator or designee must ensure that only patients who meet all the following inclusion and none of the exclusion criteria are offered treatment in the study.

5.2 Inclusion criteria

Patients eligible for inclusion in this study have to meet **all** of the following criteria:

1. Age \geq 15 years old at time of informed consent.
2. Diagnosis of teratoma for which no additional standard surgical or medical therapy exists.
3. Availability of an archival or newly obtained tumor sample (collected at diagnosis or progression) with accompanying pathology report.
 - Patients without a tumor sample may be permitted to participate after discussion between Novartis and the investigator.
4. Patients must have completed at least 1 prior line of chemotherapy for germ cell tumor (except patients who present with primary, pure teratoma who need not have received any previous chemotherapy)
5. Radiographic progression, defined by RECIST v.1.1, after the last cancer treatment and within 12 weeks prior to enrollment, compared with scans within 1 year of enrollment.
6. Measurable or evaluable extra-cranial disease as defined by RECIST v.1.1.
7. Patients must have ECOG performance status of 0-1.
8. Written informed consent/assent before any study-specific screening procedures. For pediatric patients, consent will be obtained from parent(s) or legal guardian(s) and the signature of at least 1 parent or guardian will be required. Investigators will also obtain assent of patients according to local, regional or national guidelines.

5.3 Exclusion criteria

Patients eligible for this study must not meet **any** of the following criteria:

1. CNS disease unless radiation therapy and/or surgery has been completed and serial evaluation by CT (with contrast enhancement) or MRI over a minimum of 2 months demonstrates stable disease. Patient must be asymptomatic and without need for treatment with systemic corticosteroids or anti-epileptic medications.
2. Malignant germ cell tumors other than that being treated in this study, including tumors with elements of mixed histology such as embryonal carcinoma, choriocarcinoma, yolk sac tumor or seminoma. Note – this refers to the histology at the time of enrollment, not the histology at the time of initial presentation.
3. Pathologic evidence of malignant transformation.
4. Concurrent malignancy other than teratoma within 3 years of randomization, with the additional exceptions treated NSGCT from which teratoma has emerged, of adequately treated basal or squamous cell carcinoma of the skin, curatively resected cervical cancer or curatively resected carcinoma *in situ* of any type.
5. Prior treatment with any CDK4/6 inhibitor therapy
6. Any concurrent severe and/or uncontrolled medical condition that, in the investigator's judgment serves as a contraindication to patient participation (e.g., chronic pancreatitis, active hepatitis, viral hepatitis or known HIV positivity). Baseline HIV screening is not required.
7. Patients who have not recovered to \leq CTCAE grade 1 from the acute toxic effects (except for alopecia) of all prior chemotherapy, immunotherapy, or radiotherapy.

8. Impaired gastrointestinal (GI) function or GI disease that may significantly alter the absorption of the study drug (e.g., ulcerative diseases, uncontrolled nausea, vomiting, diarrhea, malabsorption syndrome, or small bowel resection).
9. Impaired cardiac function or any clinically significant cardiac disease, including any of the following:
 - Left ventricular ejection fraction (LVEF) < 45% or less than the institution's lower limit of normal as determined by multiple gated acquisition scan (MUGA) or echocardiogram (ECHO)
 - Congenital long QT syndrome or family history of unexpected sudden cardiac death
 - QT corrected with Fridericia's (QTcF) QTcF >450 msec for males and >470 msec for females on screening ECG
 - Clinically significant heart disease such as CHF requiring treatment (NYH grade ≥ 2), unstable angina pectoris or myocardial infarction within the past 3 months. Any other clinically significant heart disease such as unstable arrhythmia, resting bradycardia, right bundle branch block, bifascicular block, or any heart disease that requires the use of a cardiac pacemaker ≤ 3 months prior to starting study drug.
 - Patients who are currently receiving medications with known risk of prolonging the QT interval or inducing Torsades de Pointes and are unable to discontinue or switch to an alternate medication.
10. Concomitant therapy that precludes enrollment:
 - Systemic antineoplastic therapy or any experimental therapy within 3 weeks before the first dose of study drug (6 weeks for prior nitrosoureas, bevacizumab, or mitomycin C).
 - Systemic corticosteroids within 2 weeks prior to starting study drug. Note: Corticosteroids are permitted for use as single doses, topical applications (e.g., for rash), inhaled sprays (e.g., for obstructive airways diseases), eye drops or local injections (e.g., intra-articular).
11. Major surgery within 2 weeks of the first dose of study drug (mediastinoscopy, insertion of a central venous access device, or insertion of a feeding tube is not considered major surgery)
12. Received radiotherapy ≤ 4 weeks or limited field radiation for palliation ≤ 2 weeks prior to randomization, or patient has not recovered to \leq CTCAE grade 1 related toxicity.
13. Requirement for treatment with any of the prohibited medications including strong CYP3A4/5 inhibitors, strong CYP3A4/5 inducers, CYP3A4/5 substrates with a narrow therapeutic index, and medications with strong risk of QT prolongation ([Appendix 4](#)).
14. Participation in a prior investigational study within 30 days prior to enrollment or within 5-half-lives of the investigational product, whichever is longer.
15. Have any of the following out-of-range laboratory values:
 - Absolute neutrophil count $\leq 1.5 \times 10^9/L$
 - Platelet count $\leq 100 \times 10^9/L$
 - Hemoglobin ≤ 9.0 g/dL
 - Potassium unless correctable by oral supplementation

- Calcium (corrected for serum albumin) unless correctable by oral supplementation
 - Magnesium unless correctable by oral supplementation
 - Serum creatinine $\geq 1.5 \times$ ULN
 - Alanine aminotransferase (AST) and aspartate aminotransferase (ALT) $> 2.5 \times$ ULN for age; for patients with liver metastases $\geq 5 \times$ ULN for age.
 - Total serum bilirubin $>$ ULN except for patients with Gilbert's syndrome who may only be included if the total bilirubin is $\geq 1.5 \times$ ULN INR ≥ 1.5
16. Pregnant or nursing (lactating) women, where pregnancy is defined as the state of a female after conception and until the termination of gestation, confirmed by a positive hCG laboratory test.
17. Women of child-bearing potential, defined as all women physiologically capable of becoming pregnant, **unless** they are using highly effective methods of contraception during dosing and for 3 weeks after stopping dosing. Highly effective contraception methods include:
- Total abstinence (when this is in line with the preferred and usual lifestyle of the patient), periodic abstinence (e.g., calendar, ovulation, symptothermal, post-ovulation methods), and withdrawal are not acceptable methods of contraception.
 - Female sterilization (have had surgical bilateral oophorectomy with or without hysterectomy) or tubal ligation at least six weeks before starting study drug. In case of oophorectomy alone, only when the reproductive status of the female has been confirmed by follow-up hormone level assessment.
 - Male sterilization (at least 6 months prior to screening). For female patients on the study the vasectomized male partner should be the sole partner for that patient.
 - Combination of any two of the following (a+b or a+c, or b+c):
 - a. Use of oral, injected or implanted hormonal methods of contraception or other forms of hormonal contraception that have comparable efficacy (failure rate $< 1\%$), for example hormone vaginal ring or transdermal hormone contraception.
 - b. Placement of an intrauterine device (IUD) or intrauterine system (IUS).
 - c. Barrier methods of contraception: Condom or Occlusive cap (diaphragm or cervical/vault caps) with spermicidal foam/gel/film/cream/vaginal suppository
- In case of use of oral contraception females should have been stable on the same oral contraceptive for a minimum of 3 months before starting study drug.
18. Women are considered post-menopausal and not of child bearing potential if they have had 12 months of natural (spontaneous) amenorrhea with an appropriate clinical profile (e.g., age appropriate, history of vasomotor symptoms) or have had surgical bilateral oophorectomy (with or without hysterectomy) or tubal ligation at least six weeks ago. In the case of oophorectomy alone, only when the reproductive status of the woman has been confirmed by follow-up hormone level assessment is she considered not of child bearing potential.
19. Sexually active males, unless they use a condom during intercourse, while taking study drug and for 3 weeks after stopping study drug and should not father a child during this

period. A condom is required to be used also by vasectomized men in order to prevent delivery of the drug via seminal fluid.

6 Treatment

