	
adequately treated basal or squamous cell carcinoma of the skin, curatively resected cervical cancer or curatively resected carcinoma in situ of any type
 
5. Prior treatment with any CDK4/6 inhibitor therapy
 
6. Any concurrent severe and/or uncontrolled medical condition that, in the investigator's judgment serves as a contraindication to patient participation (e.g., chronic pancreatitis, active hepatitis, viral hepatitis or known HIV positivity). Baseline HIV screening is not required
 
7. Patients who have not recovered to \leq CTCAE grade 1 from the acute toxic effects (except for alopecia) of all prior chemotherapy, immunotherapy, or radiotherapy
 
6. Impaired gastrointestinal (GI) function or GI disease that may significantly alter the absorption of the study drugs (e.g., ulcerative diseases, uncontrolled nausea, vomiting, diarrhea, malabsorption syndrome, or small bowel resection)
 
9. Impaired cardiac function or any clinically significant cardiac disease, including any of the following
 
• Left ventricular ejection fraction (LVEF) $< 45\%$ or less than the institution's lower limit of normal as determined by multiple gated acquisition scan (MUGA) or echocardiogram (ECHO)• Congenital long QT syndrome or family history of unexpected sudden cardiac death• QT corrected with Fridericia's (QTcF) $QTcF > 450$ msec for males and > 470 msec for females on screening ECG• Clinically significant heart disease such as CHF requiring treatment (NYH grade ≥ 2), unstable angina pectoris or myocardial infarction within the past 3 months. Any other clinically significant heart disease such as unstable arrhythmia, resting bradycardia, right bundle branch block, bifascicular block, or any heart disease that requires the use of a cardiac pacemaker ≤ 3 months prior to starting study drug• Patients who are currently receiving medications with known risk of prolonging the QT interval or inducing Torsades de Pointes and are unable to discontinue or switch to an alternate medication 
10. Concomitant therapy that precludes enrollment
 
• Systemic antineoplastic therapy or any experimental therapy within 3 weeks before the first dose of study drug (6 weeks for prior nitrosoureas, bevacizumab, or mitomycin C)• Systemic corticosteroids within 2 weeks prior to starting study drug. Note: Corticosteroids are permitted for use as single doses, topical applications (e.g., for rash), inhaled sprays (e.g., for obstructive airways diseases), eye drops or local injections (e.g., intra-articular) 
11. Major surgery within 2 weeks of the first dose of study drug (mediastinoscopy, insertion of a central venous access device, or insertion of a feeding tube is not considered major surgery)
 
12. Received radiotherapy ≤ 4 weeks or limited field radiation for palliation ≤ 2 weeks prior to randomization, or patient has not recovered to \leq CTCAE grade 1 related toxicity
 
13. Requirement for treatment with any of the prohibited medications including strong CYP3A inhibitors, strong CYP3A inducers, CYP3A substrates with a narrow therapeutic index, and medications with strong risk of QT prolongation
 
14. Have any of the following out-of-range laboratory values
 
• Absolute neutrophil count $< 1.5 \times 10^9/L$• Platelet count $< 100 \times 10^9/L$• Hemoglobin < 9.0 g/dL• Potassium unless correctable by oral supplementation• Calcium (corrected for serum albumin) unless correctable by oral supplementation• Magnesium unless correctable by oral supplementation• Serum creatinine $\geq 1.5 \times ULN$• Alanine aminotransferase (AST) and aspartate aminotransferase (ALT) $> 3 \times ULN$ for age; for patients with liver metastases $\geq 5 \times ULN$ for age.• Total serum bilirubin $> 1.5 \times ULN$; or total bilirubin $\geq 3.0 \times ULN$ with direct bilirubin within normal range in patients with well documented Gilbert's Syndrome• INR ≥ 1.5

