7.1 Study flow and visit schedule

Table 7-1 lists all of the assessments and indicates with an “X”, the visits when they are performed. All data obtained from these assessments must be supported in the patient’s source documentation.

No eCRF will be used as a source document.

[figure not shown]
After the screening period, all assessments have a ± 3 day window unless otherwise indicated

If study drug is being held due to toxicity, then the scheduled visits and assessments should still be performed per protocol, unless otherwise specified. Additional assessments may be performed as clinically indicated.

[REDACTED]

Table 7-1 Visit evaluation schedule

	Category	Protocol Section	Screening	Treatment Cycles							EOT	Crossover cycles						Crossover EOT	Follow-Ups				
				Cycle 1				Cycle 2		Subsequent Cycles		Cycle 1				Cycle 2			Subsequent Cycles	30-Day	Progression	Survival	
				1	8	15	21	1	21			1	8	15	21	1	21						1
Day of cycle			-14 to-1	1	8	15	21	1	21	1		1	8	15	21	1	21	1					
Obtain informed consent	D	7.1.1	X																				
IVRS/IRT registration	D	4.1	X																				
Demography	D	7.1.1.3	X																				
Inclusion/exclusion criteria	D	5.2 / 5.3	X									X											
Medical history	D	7.1.1.3	X																				
Diagnosis and extent of cancer	D	7.1.1.3	X																				
Prior antineoplastic therapy	D	7.1.1.3	X																				
Physical examination	S	7.2.2.1	X	X	X	X	X	X		X	X	X	X	X	X			X					
ECOG performance status	D	7.2.2.4	X	X				X		X	X	X			X		X	X					
Height	D	7.2.2.3	X																				
Weight	D	7.2.2.3	X	X				X		X	X	X			X		X	X					
Vital signs	D	7.2.2.2	X	X	X	X	X	X	X	X	X	X	X	X	X	X	X	X	X				

	Category	Protocol Section	Screening	Treatment Cycles							EOT	Crossover cycles						Crossover EOT	Follow-Ups				
				Cycle 1				Cycle 2				Subsequent Cycles	Cycle 1				Cycle 2		Subsequent Cycles	30-Day	Progression	Survival	
				1	8	15	21	1	21	1			1	8	15	21	1						21
Day of cycle			-14 to-1	1	8	15	21	1	21	1		1	8	15	21	1	21	1					
Hematology	D	7.2.2.5.1	X	X		X	X	X	X	X	X	X		X	X	X		X	X				
Chemistry	D	7.2.2.5.2	X	X		X	X	X	X	X	X	X		X	X	X		X	X				
Thyroid panel	D	7.2.2.5.3	X								X							X					
Coagulation	D	7.2.2.5.4	X								X							X					
Pregnancy test	D	7.2.2.5.5	X	X				X		X	X	X				X		X	X				
ECG	D	7.2.2.6.1	X	X	X	X		X	X	X	X	X	X		X	X	X	X					
Cardiac imaging (MUGA/ECHO)	D	7.2.2.6.2	X								X							X					
Collection of archival paraffin blocks/slides or newly obtained tumor sample	D	7.2.4.1	X																				

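### The protocol summary and Section 5.3 set different AST/ALT and bilirubin exclusion limits, and the printed Section 5.3 Gilbert's clause needs a source check

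*Protocol*

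**What the plan says.** **AST/ALT.** Protocol Section 5.3, criterion 15, excludes patients without liver metastases who have "aspartate aminotransferase (ALT) $> 2.5 \times$ ULN for age". The protocol summary, criterion 14, has "aspartate aminotransferase (ALT) $> 3 \times ULN$ for age". Both lists transpose the abbreviations AST and ALT, which is harmless here because one limit covers both enzymes. With liver metastases, both lists exclude at 5 × ULN or more.

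**Bilirubin.** Section 5.3 reads "Total serum bilirubin $>$ ULN except for patients with Gilbert", and continues for those patients: "syndrome who may only be included if the total bilirubin is $\geq 1.5 \times$ ULN". The summary reads "Total serum bilirubin $> 1.5 \times ULN$; or total bilirubin $\geq 3.0 \times ULN$ with direct bilirubin within normal range", with the second limb confined to well-documented Gilbert's syndrome.

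**Which list governs.** Section 5.1 introduces the criteria that come after it by requiring that "only patients who meet all the following inclusion and none of the exclusion criteria are offered treatment in the study". In Table 7-1, the row "Inclusion/exclusion criteria" cites Sections 5.2 and 5.3. It is marked at screening and again at crossover Cycle 1 Day 1.

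**Status.** Amendment 3 says that enrolment was halted on 20-Nov-2015 with 10 patients enrolled. On 18-Aug-2017 four were on treatment: three still blinded and one already crossed over.

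**The concern.** The change lists for Amendments 1 and 2 both say the Section 5.2 and 5.3 criteria were put into the summary for consistency, so the two lists were meant to agree. They do not. Someone screening from the summary would apply looser AST/ALT and bilirubin limits than the operative section allows.

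These are safety limits for a drug whose hepatic monitoring was tightened in Amendment 2 because of possible drug-induced liver injury. If the printed Gilbert's sign is what the source says, the clause followed literally turns away a mildly raised bilirubin and accepts any higher one.

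Two uses of the limits may remain: the eligibility check at crossover, and the listing of protocol deviations that SAP Section 4 keeps.

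**Working it through.** The plan gives no calculated figure on this point, so the check sets the two rules side by side. All values are multiples of ULN.

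**Step 1: limits that do not depend on how a sign was read.**

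| Item | Section 5.3 admits | Summary admits | Lists disagree |
|---|---|---|---|
| AST/ALT, no liver metastases | up to 2.5 | up to 3.0 | above 2.5, up to 3.0 |
| AST/ALT, liver metastases | below 5 | below 5 | nowhere |
| Total bilirubin, no Gilbert's | up to 1.0 | up to 1.5 | above 1.0, up to 1.5 |

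For example, AST/ALT of 2.75 without liver metastases, or bilirubin of 1.2 without Gilbert's, passes the summary and fails Section 5.3. The differences are in the digits (2.5 against 3, and 1 against 1.5). A misread inequality sign cannot produce them.

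**Step 2: Gilbert's syndrome with normal direct bilirubin.** Two things are uncertain. The Section 5.3 sign may be as printed or may be meant as ≤. The summary's 3.0 limb may be read literally, so that the 1.5 limb still excludes these patients, or as an exception to the 1.5 limb. Values at or below ULN are taken as admitted. This is an assumption, because the word only in Section 5.3 could be pressed to bar those values too.

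| Section 5.3 sign | Summary limb | Section 5.3 admits | Summary admits | Lists disagree |
|---|---|---|---|---|
| ≥ as printed | literal | ≤ 1.0 or ≥ 1.5 | ≤ 1.5 | between 1.0 and 1.5; all above 1.5 |
| ≥ as printed | exception | ≤ 1.0 or ≥ 1.5 | < 3.0 | between 1.0 and 1.5; 3.0 and above |
| ≤ if meant | literal | ≤ 1.5 | ≤ 1.5 | nowhere |
| ≤ if meant | exception | ≤ 1.5 | < 3.0 | between 1.5 and 3.0 |

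Correcting the sign alone therefore reconciles the lists on only one reading of the summary.

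**Step 3: how firm the printed sign is.** The clause runs straight into the INR item on the same line, so a bullet was lost when the PDF was read. Neighbouring signs also differ between the lists. Section 5.3 has "Absolute neutrophil count $\leq 1.5 \times 10^9/L", while the summary uses a strict less-than for the same count; platelets and haemoglobin show the same difference. The text available cannot tell an authoring error from a reading error.

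**Step 4: which values the rest of the protocol supports.** In Table 6-4, grade 2 begins above 3.0 × ULN for AST/ALT and above 1.5 × ULN for bilirubin. Those are the summary's cut-offs. Table 6-4 also applies bilirubin dose changes in Gilbert's patients to direct bilirubin only. The summary's Gilbert's limb has a direct-bilirubin condition and the Section 5.3 clause has none.

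**Step 5: reach.** Four patients on treatment less one already crossed over leaves 4 − 1 = 3 still blinded. Their arms are not given, so 0 to 3 could still cross over from placebo.

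**The case against.** The strongest reply is that almost nothing now turns on this. No patient remains to be screened for entry. Amendment 3 lets placebo patients cross over on the investigator's judgment of clinical interest. Section 6.4.2 refers to criteria for crossover as if they were separate, and Section 4.1.6, which may define them, is not visible. SAP Table 2-2 excludes no patient from any analysis set for a laboratory eligibility deviation, and SAP Section 4 cancels the PFS analysis. Table 6-4 keeps the dose unchanged at grade 1 bilirubin (above ULN to 1.5 × ULN) with bi-weekly liver tests, so the safety weight of the ordinary bilirubin gap is small. All of this stands. It limits the severity but does not remove the contradiction.

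The reply is also right on two stronger readings that a reader might infer:

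- **That Section 5.3 certainly admits Gilbert's patients with unlimited bilirubin.** The printed text says so, but Step 3 shows that a reading error cannot be ruled out.
- **That the Section 5.3 values are the intended ones and the summary is simply wrong.** Section 5.1 and Table 7-1 show which list governs, not which numbers were meant. The match between Table 6-4 and the summary points the other way.

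**Conclusion.** The point holds, as a minor one. The two current lists conflict on AST/ALT above 2.5 and up to 3.0 × ULN without liver metastases, and on total bilirubin above 1.0 and up to 1.5 × ULN without Gilbert's syndrome. Both conflicts are certain from the text. The Gilbert's clause is defective as printed, but whether the source has the same defect is open. So is the extent of any conflict there, which depends on the reading taken.

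A reader might go further and infer that patients were enrolled under the wrong limits. The documents do not support that: they show neither the limits in force when the 10 patients were screened nor any patient with liver values in these zones. Power, type I error and the efficacy analyses are unaffected. What remains is the possible crossover check for 0 to 3 patients, if Section 4.1.6 does not set its own criteria, and the deviation listing.

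**What to change.** 1. State one set of AST/ALT and bilirubin limits in both places. Use Section 5.3 as the default, because it governs and is the stricter list on both core limits (AST/ALT above 2.5 × ULN without liver metastases; bilirubin above ULN without Gilbert's). Have the clinical team confirm the values first, since the Table 6-4 grade 2 cut-offs match the summary.
2. Check the Gilbert's sign in the source document. If it also shows ≥, rewrite the clause as a ceiling, with the clinical team setting the value and any direct-bilirubin condition.
3. In both lists, write the Gilbert's rule as an explicit exception to the general bilirubin limit, with the same ceiling.
4. Unless Section 4.1.6 already does so, state whether these limits apply at the crossover Cycle 1 Day 1 eligibility check in Table 7-1.

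The cost is a few wording corrections. Section 12.1 requires a written amendment for any change, so they are best bundled with another amendment; the source check needs none. Sample size, analysis and past screening decisions do not change.
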